 - For subjects taking 6-MP, the dose should not exceed 1 mg/kg/day.
 - For subjects taking IM/SC MTX, dose should not exceed 25 mg per week.
 - Note: Oral MTX use is allowed during the study (at a stable dose for 28 days prior to Baseline), however use of oral MTX is not sufficient for inclusion into the study.

Note: If a subject is on both an oral corticosteroid and an immunosuppressant listed above, BOTH of the drugs need to meet the above criteria.

and/or

- Concurrent therapy with corticosteroids or the above-mentioned immunosuppressants (azathioprine, 6-MP or IM/SC MTX) is not required for subjects not currently taking these medications who were previously treated during the past 2 years and have confirmed documentation of failure to respond, or were previously treated during the past 5 years and have confirmed documentation indicating lack of tolerability.
5. Subject has a negative TB Screening Assessment. If the subject has evidence of a latent TB infection during the Screening Assessment, the subject must initiate and complete a minimum of 3 weeks (or per local guidelines, whichever is longer) of an ongoing TB prophylaxis prior to Baseline (Section 5.3.1).
 6. If female subject, is either not of childbearing potential, defined as postmenopausal for at least 1 year or surgically sterile (bilateral tubal ligation, bilateral oophorectomy and/or hysterectomy) or is of childbearing potential and is practicing an approved method of birth control throughout the study and for 150 days after last dose of study drug.

Examples of approved methods of birth control include the following (see local informed consent for more detail):
 - Condoms, sponge, foams, jellies, diaphragm or intrauterine device (IUD);
 - Hormonal contraceptives for 90 days prior to study drug administration;
 - A vasectomized partner.
 7. Subject must be able and willing to give written informed consent and to comply with the requirements of this study protocol.
 8. Subject is judged to be in otherwise good health as determined by the Principal Investigator (or designee) based upon the results of medical history, laboratory profile, physical examination, CXR, and a 12-lead electrocardiogram (ECG) performed during Screening.
 9. Subject must be able and willing to self-administer subcutaneous (SC) injections or have a qualified person available to administer SC injections.

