5.2.3.2 Concomitant Therapy

Subjects taking immunomodulators at Baseline will continue their dose of azathioprine, 6-MP, MTX or any other immunomodulators during the study, provided they are on a stable dose of the medication for at least 28 days prior to Baseline (Week 0). Doses of these concomitant medications (azathioprine, 6-MP, MTX, or other immunomodulators) must remain stable throughout the duration of the study, except in the event of treatment-related toxicities (e.g., leukopenia or elevated liver enzymes) considered moderate to severe in the opinion of the investigator.

Subjects taking aminosaliclates at Baseline will continue aminosaliclates during the study, provided they are on stable doses of the medication for at least 28 days prior to Baseline (Week 0). Doses of oral aminosaliclates must remain stable throughout the duration of the study, except in the event of treatment-related toxicities considered moderate to severe in the opinion of the investigator.

Subjects taking corticosteroids at Baseline will continue their dose of corticosteroids during the study, provided they are on a stable dose prior to Baseline (Week 0) as outlined in inclusion criterion 4 in Section 5.2.1. Subjects will not be permitted to change the

corticosteroid dose during the first 4 weeks of the study, except in the event of treatment-related toxicities considered moderate to severe in the opinion of the investigator. At Week 4, all subjects will have their dose tapered according to the schedule in Section 5.3.1.1. The steroid taper is mandatory and deviations from the taper (or increases in steroid doses) are not permitted. If the Investigator feels that the steroid taper is not advisable for a particular subject at Week 4, the subject must be withdrawn from the study.

- For steroids other than budesonide, a reduction of 5 mg prednisone (or equivalent) per day for doses > 10 mg/day of prednisone (or equivalent) every week until a 10 mg/day (or equivalent) dose is reached, then a weekly decrease by 2.5 mg (or equivalent) per day until discontinuation.
- For budesonide, a weekly decrease by 3 mg/day of budesonide until discontinuation.

Subjects may **not** be on both oral budesonide and oral prednisone (or equivalent) simultaneously.

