Week 22	155	149 – 162
Week 24	169	163 – 176
Week 26	183	177 – 190

Rx Day B = date of visit – date of first dose of adalimumab + 1

- a. Date of first dose of adalimumab in double-blind treatment period.

Table 7. Visit Windows for Analysis of hs-CRP, Chemistry and Hematology (Any Adalimumab)

Visit Week	Nominal Day	Time Window (Rx Day B Range)
Week 0	1 ^a	≤ 1
Week 2	15	2 – 22
Week 4	29	23 – 36
Week 6	43	37 – 50
Week 8	57	51 – 71
Week 12	85	72 – 99
Week 16	113	100 – 127
Week 20	141	128 – 162
Week 26	183	163 – 190

Rx Day B = date of visit – date of first dose of adalimumab + 1

a. Date of first dose of adalimumab in double-blind treatment period.

Table 8. Visit Windows for Analysis of Urinalysis (Any Adalimumab)

Visit Week	Nominal Day	Time Window (Rx Day B Range)
Week 0	1 ^a	≤ 1
Week 4	29	2 – 43
Week 8	57	44 – 71
Week 12	85	72 – 112
Week 20	141	113 – 161
Week 26	183	162 – 190

Rx Day B = date of visit – date of first dose of adalimumab + 1

a. Date of first dose of adalimumab in double-blind treatment period.

Table 9. Visit Windows for Analysis of Fecal Calprotectin and IBDQ (Any Adalimumab)

Visit Week	Nominal Day	Time Window (Rx Day B Range)
Week 0	1 ^a	≤ 1
Week 4	29	2 – 43
Week 8	57	44 – 71
Week 26	183	72 – 190

Rx Day B = date of visit – date of first dose of adalimumab + 1

a. Date of first dose of adalimumab in double-blind treatment period.

Definition of Missing Data Imputation

The following imputation methods will be used to impute missing values in the efficacy analyses. In addition, an observed case analysis will be performed.

Non-Responder Imputation (NRI)

The NRI approach is used for binary efficacy variables. These variables can take values of 'Achieved' or 'Not Achieved' or may be missing for any reason including discontinuation from study. According to the NRI imputation approach, all missing value will be considered as 'Not Achieved.'

Subjects who dose-escalate from OL adalimumab 40 mg eow to OL adalimumab 80 mg eow due to disease flare or non-response will be imputed as 'Not Achieved' in the analysis of binary efficacy variables.

For the analysis of Week 26 efficacy variables only for dose-escalated subjects, the remission/response status will be determined based on the observed data at Week 26 after the dose escalation.

Last Observation Carried Forward (LOCF)

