For all variables (discrete/categorical/response variables and continuous variables), except for the endpoint defined for dose-escalated subjects only, the following rules will be used for the LOCF approach:

1. Baseline and pre-baseline values will not be used to impute the missing post-baseline values.
2. Missing values after Study Day 1 will be imputed using the latest non-missing values after Day 1 and prior to the missing value.
3. For subjects who dose-escalate to OL adalimumab 80 mg eow, the last non-missing value before dose escalation will be used for LOCF values at the following visits.

For the endpoints defined for dose-escalated subjects only, the last non-missing value through the entire study will be used for LOCF values at the following visits.

Observed Case (OC)

Observed case analysis will be performed such that missing values will not be imputed. Data from subjects who dose-escalate to OL adalimumab 80 mg eow will be considered missing after the point of dose escalation. These data will not be imputed and will not be included in the numerator or denominator.

Imputation of Missing Dates

For baseline, efficacy, and safety parameters, if the day and/or month are missing, the following conventions will be used to impute the missing dates:

- 01 for missing start day
- End of month for missing end day
- January 1st for missing start month
- December 31st for missing end month

Rule for CDAI Calculation

Up to 14 day of diaries will be recorded in eCRF or CDAI calculation for each visit. Diary entries will be evaluated for the CDAI calculation for each visit. For each CDAI subscore, the available scores from the most recent diary days (at least 4 days, up to

7 days) prior to actual day of the study visit will be summed, and then multiplied by the corresponding multiplier to get subtotal score. If available diary entries are fewer than 7 days, the subtotal score will be calculated as (summed total available score/number of days) \times 7 \times corresponding multiplier. The three subscores (number of liquid/very soft stools, abdominal pain rating, and general well-being) will then be rounded to one decimal. The final CDAI is rounded to a whole number.

If a subject has fewer than 4 days of diary data, the total CDAI score will not be calculated and will be considered missing.

If a subject has any subscore missing, the corresponding total CDAI score will be missing.

Definition of Clinical Remission

CDAI $<$ 150.

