10.3 Secondary Efficacy Analyses

The Week 26 efficacy endpoint is proportion of subjects who achieve clinical remission at Week 26 (CDAI < 150) in subjects who achieved clinical response (decrease in CDAI ≥ 70 points from Baseline) at Week 8. The one sample Exact test will be performed by comparing it to the clinically meaningful remission rate of 30%, and the two-sided 95% CI will be provided.

Key secondary efficacy endpoints include:

- Proportion of subjects who achieve CDAI < 150 plus a reduction in hs-CRP of at least 50% from Baseline at Week 4.
- Proportion of subjects who achieve CDAI < 150 plus a reduction in hs-CRP of at least 50% from Baseline at Week 26 in subjects who achieved decrease in

CDAI \geq 70 points from Baseline plus at least 30% reduction in hs-CRP from Baseline at Week 8.

- Proportion of subjects who discontinue corticosteroid use and achieve clinical remission (CDAI $<$ 150) at Week 26 in subjects who were taking steroids at Baseline and who achieved clinical response (decrease in CDAI \geq 70 points from Baseline) at Week 8.
- Proportion of subjects who discontinue corticosteroid use and achieve CDAI $<$ 150 plus a reduction in hs-CRP of at least 50% from Baseline at Week 26 in subjects who were taking steroids at Baseline and who achieved decrease in CDAI \geq 70 points from Baseline plus a reduction in hs-CRP of at least 30% from Baseline at Week 8.
- Proportion of subjects who achieve clinical response (decrease in CDAI \geq 70 points from Baseline) at Week 4.
- Proportion of subjects who achieve decrease in CDAI \geq 70 points from Baseline plus a reduction in hs-CRP of at least 30% from Baseline at Week 4.
- Proportion of subjects who achieve CDAI $<$ 150 and hs-CRP $<$ 3 mg/L at Week 4.
- Proportion of subjects who achieve CDAI $<$ 150, hs-CRP $<$ 3 mg/L at Week 26 in subjects who achieved clinical response (decrease in CDAI \geq 70 points from Baseline) at Week 8.
- Proportion of subjects who achieve IBDQ remission (IBDQ \geq 170 points) at Week 4.
- Proportion of subjects who achieve IBDQ remission at Week 26 in subjects with clinical response (decrease in CDAI \geq 70 points from Baseline) at Week 8.
- Change from Baseline in fecal calprotectin level at Week 4.
- Proportion of subjects who achieve CDAI $<$ 150, hs-CRP $<$ 3 mg/L and fecal calprotectin $<$ 250 μ g/g at Week 4.

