- Proportion of subjects who achieve CDAI $<$ 150, hs-CRP $<$ 3 mg/L and fecal calprotectin $<$ 250 μ g/g at Week 26 in subjects who achieved clinical response (decrease in CDAI \geq 70 points from Baseline) at Week 8.

Additional secondary endpoints include:

- Proportion of subjects with clinical remission (CDAI < 150) over time.
- Proportion of subjects with CDAI < 150 plus a reduction in hs-CRP of at least 50% from Baseline over time.
- Proportion of subjects with clinical response (decrease in CDAI \geq 70 points from Baseline) over time.
- Proportion of subjects with decrease in CDAI \geq 70 points from Baseline plus a reduction in hs-CRP of at least 30% from Baseline over time.
- Change from Baseline in CDAI over time.
- Change from Baseline in hs-CRP level over time.
- Change from Baseline in fecal calprotectin level over time.

The analysis over time will be performed for the DB placebo-controlled period (Week 0 to Week 4), with comparisons between active treatment and placebo groups. The analysis over time will also be performed for Any Adalimumab set (the entire study on or after the first dose of adalimumab), with only summary statistics for adalimumab treatment.

Exploratory endpoints include:

- Proportions of subjects who achieve CDAI < 150 at Week 26 in subjects who did not achieve clinical response (decrease in CDAI \geq 70 points from Baseline) at Week 8.

For categorical endpoints with comparison between the treatment groups, the difference in proportions of subjects between treatment groups will be analyzed using the CMH test adjusted for stratification variables. Additionally, the CMH based two-sided 95% confidence interval for the difference in proportions will be provided. For categorical endpoints with comparison to the clinically meaningful constant rate, the one sample Exact test will be performed and the two-sided 95% CI will be provided. The NRI imputation method will be used for subjects with missing data at the time point

evaluated. Subjects who dose-escalate will be imputed using NRI for visits after dose escalation. The LOCF method will also be used as the sensitivity analyses.

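### Week 26 clinical remission: the SAP has no scoring rule for Crohn's therapy added during the study, other than escalation to 80 mg, so a remission reached with such help counts as maintenance by adalimumab

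*SAP*

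**What the plan says.** SAP 6.0, under non-responder imputation, gives two reasons for failure on a binary endpoint. The first is missing data: "According to the NRI imputation approach, all missing value will be considered as" not achieved. The second is escalation: "Subjects who dose-escalate from OL adalimumab 40 mg eow to OL adalimumab 80 mg eow due to disease flare or non-response will be imputed as" failures. SAP 10.3 repeats the second rule ("Subjects who dose-escalate will be imputed using NRI for visits after dose escalation"), and Protocol 8.1.4 has the same two. LOCF also singles out escalation: "the last non-missing value before dose escalation will be used for LOCF values at the following visits". Clinical remission is CDAI < 150, with no condition on concomitant treatment.

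For Week 26 clinical remission in Week 8 responders, SAP 10.3 states: "The one sample Exact test will be performed by comparing it to the clinically meaningful remission rate of 30" per cent. There is no concurrent control at that point. SAP 5.1 makes ITT the efficacy population and defines no per-protocol set. Concomitant medications and deviations are only summarised (SAP 7.3 and 8.0).

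**The concern.** The SAP treats a need for more adalimumab as failure of 40 mg maintenance. A need for a different Crohn's drug tells the reader much the same about maintenance, yet no rule covers it. A Week 8 responder who stays in the study without escalating, receives another Crohn's therapy and then has CDAI < 150 is scored as a remitter, and the result is read as maintenance by adalimumab.

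This matters more here than in a controlled comparison because no parallel arm is scored by the same rule. Week 26 remission is listed as a secondary endpoint, but maintenance is part of the primary objective (SAP 4.1).

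**Working it through.** **Step 1. Can it happen under the protocol?**

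- Entry. Criterion 4 in Protocol 5.2.1 admits subjects taking neither steroids nor immunosuppressants: concurrent therapy "is not required for subjects not currently taking these medications who were previously treated during the past 2 years" with documented failure, or within 5 years with documented intolerance.
- Stable-dose rules. Protocol 5.2.3.2 addresses those already on a drug, for example "Subjects taking corticosteroids at Baseline will continue their dose of corticosteroids during the study". Its rules for immunomodulators, aminosalicylates and Crohn's antibiotics are framed in the same way.
- Prohibited list. Protocol 5.2.3.3 covers biologics, IV steroids, rectal therapy, cyclosporine, tacrolimus, mycophenolate, tofacitinib, thalidomide, systemic traditional Chinese medicine, live vaccines and investigational agents. It does not list starting an oral steroid, azathioprine, 6-MP, methotrexate, an aminosalicylate or a Crohn's antibiotic.
- Escalation. This needs Week 12 or later, CDAI of at least 200 and an hs-CRP criterion (Protocol 5.3.1.1). A subject with CDAI 150 to 199 is neither in remission nor eligible to escalate. The rule to escalate or withdraw is written for subjects who have tapered steroids.
- Prohibited drugs. Under Protocol 5.4.1 their use leads to withdrawal only if the sponsor's physician judges that continuing puts the subject at risk. It is a reportable deviation (Protocol 7.0), but that does not alter endpoint scoring.
- Steroid-free endpoints. The two Week 26 endpoints that require steroid discontinuation do not fill the gap. They are assessed "at Week 26 in subjects who were taking steroids at Baseline and who achieved clinical response" (the second also requires an hs-CRP reduction), so subjects off steroids at Baseline are outside them.

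**Step 2. Reproduce the plan's figure.** Inputs from SAP 4.3: n = 100, null rate 30%, alternative 52%, exact test, two-sided 0.05. The success probability is P(X ≥ r | n, p) = Σ C(n,k) p^k (1−p)^(n−k), summed over k = r to n.

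- 39 remitters: two-sided exact p = 0.063 (upper tail 0.034).
- 40 remitters: two-sided exact p = 0.0375 (upper tail 0.021).
- So r = 40, and P(X ≥ 40 | 100, 0.52) = 99.4%. The stated power of at least 99% is correct.

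**Step 3. Effect of assisted remissions.** The documents give no frequency, so the assisted share is an assumption. An assisted point means a remission that would not have occurred without the added drug.

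| Unaided rate | Assumed assisted points | Rate as scored | P(at least 40 of 100) |
|---|---|---|---|
| 30% | 0 | 30% | 2.1% |
| 30% | 1 | 31% | 3.5% |
| 30% | 2 | 32% | 5.6% |
| 30% | 5 | 35% | 17.2% |
| 25% | 5 | 30% | 2.1% |

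**Step 4. Margin at the planned rate.** 52 − 40 = 12 remitters.

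**Step 5. Power if assisted remissions are rescored as failures.**

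- 2 points removed: 52% − 2 = 50%, power 98.2%.
- 5 points removed: 52% − 5 = 47%, power 93.4%.

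**The case against.** The protocol already closes most of the route, and that stands. Immunomodulator and aminosalicylate doses must stay stable except for toxicity. Steroid increases are not permitted, and antibiotic doses may change only for toxicity or resistance. It would be wrong to infer that increases for worsening disease are allowed: they would be deviations. A strict reader could extend the ban on steroid increases to new starts, although it sits in a rule for subjects being tapered. Even then the event would be a deviation, still scored on its CDAI. Subjects who enter off both drug classes have documented failure or intolerance of such therapy, which makes a drug-assisted remission less likely but not impossible.

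Four further inferences are tempting, and the documents do not support them.

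- That the fixed 30% applies to every open-label endpoint. It is specified only for Week 26 clinical remission. Other one-sample endpoints refer to an unstated constant rate, and results over time in the Any Adalimumab set are summaries only.
- That the comparison with 30% can only be biased towards success. Rescoring can only lower this trial's count. But the 30% is the upper 95% confidence bound of a placebo rate from Study M02-404, and neither document says how added therapy was scored there. If assisted placebo remitters counted as successes, a stricter rule here alone would create a mismatch.
- That Protocol 6.1.7 offers a rescue route because it lets otherwise prohibited drugs be given when medically necessary. That sentence belongs to the management of infection.
- That the present rule must be replaced. Analysing off-protocol therapy as observed within ITT is defensible, and the benchmark's own rule is unknown.

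**Conclusion.** The omission is real but narrow. Followed as written, the SAP counts an observed Week 26 CDAI < 150 as maintenance by adalimumab even after another Crohn's drug was added. This can arise from a newly started oral drug that the protocol does not bar, or from increased or prohibited therapy taken as a deviation.

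The size is unknown. The 17.2% in the table needs both an unaided rate of exactly 30% and 5 assisted points, and neither comes from the documents. With an unaided rate of 25%, the same 5 points leave the chance of success at 2.1%. At the planned 52% the conclusion would survive the loss of 12 remitters. The point therefore bears on the conclusion only if the count falls near 40 of 100. It does not show that the Week 26 result will be wrong, the stated power is correct, and the Week 4 primary analysis is not affected. It is a cheap improvement worth making because the test has no concurrent control.

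**What to change.** Before database lock, add to SAP 6.0 and 10.3 a second pre-specified analysis of Week 26 clinical remission. Score not achieved from the first of:

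1. start, restart after taper, or increase above Baseline dose of a systemic corticosteroid for Crohn's disease;
2. start, restart, or increase above Baseline dose of an immunosuppressant, aminosalicylate or Crohn's antibiotic given for worsening disease, excluding changes for toxicity or antibiotic resistance and restoration of a reduced dose;
3. any therapy in Protocol 5.2.3.3 with a potential effect on Crohn's disease.

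For LOCF, carry forward the last value before the event, as is already done for escalation. Report this analysis beside the present rule, and claim maintenance above 30% without qualification only if both agree. Apply the same scoring descriptively to the other Week 26 binary endpoints. Leave the Week 4 primary analysis and clinical conduct as they are.

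The cost is SAP wording and programming. Protocol 5.2.3 already has every medication recorded with reason, dates and dose, so no new data are needed. The downside is a slightly lower remission rate in the added analysis, with the modest loss of power shown in Step 5.

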7.1 Demographic and Baseline Characteristics

For subjects in analysis ITT set, demographic information and baseline values will be summarized by descriptive statistics. Categorical data will be summarized by number and percent; and quantitative data will be presented by n, mean, standard deviation, minimum value, median, and maximum value.

For ITT analysis set, demographics and baseline values will be compared between treatment groups and a p-value will be provided. In general, continuous variables will be analyzed using analysis of variance (using SAS procedure 'PROC GLM') with treatment group as factor. Categorical variable will be analyzed using chi-square test or Fisher's exact test if \geq 20% of the cells have expected cell count $<$ 5.

The following demographic and baseline values will be summarized.

Continuous Variables:

- Age (years)
- Body weight (kg)
- Height (cm)
- Body Mass Index (kg/m²)
- Blood Pressure (Systolic/Diastolic) (mmHg)
- Pulse (bpm)
- Respiratory Rate (RPM)
- Temperature (°C)
- CDAI score
- Crohn's Disease Duration (years)
- hs-CRP (mg/L)
- Fecal Calprotectin (µg/g)
- Albumin Concentration (mg/mL)
- IBDQ score

Categorical Variables:

- Sex (male, female)
- Age (≤ median, > median)
- Baseline Fecal Calprotectin (≤ median, > median)
- Baseline Corticosteroid Use (yes, no)
- Baseline Immunosuppressant Use (yes, no)
- hs-CRP at Baseline (< 10, ≥ 10 mg/L)
- hs-CRP at Baseline (≤ median, > median)
- Crohn's Disease Severity (CDAI ≤ 300, > 300) at Baseline
- Baseline CDAI (≤ median, > median)
- Weight (≤ median, > median)

- Baseline Albumin Concentration (\leq median, $>$ median)
- Disease Duration (\leq median, $>$ median)
- Tobacco Use (user, ex-user, never used, unknown)
- Alcohol Use (drinker, ex-drinker, non-drinker, unknown)

